Brief Summary	Phthalates and bisphenols have been detected in a range of infant care products. This pilot study will test whether intervening on these sources of exposure during the critical period of minipuberty affects infants' body burden of phthalates and bisphenols. We will recruit 10 participants from the ongoing NYU Children's Health and Development Study (CHES) cohort study who are >=37 weeks gestation or <6 months postpartum, carrying a singleton fetus or with a singleton infant, and intending to breastfeed or breastfeeding. We will randomly assign them to use either conventional baby products or phthalate- and bisphenol-free baby products for the first or next three months of their children's lives. Toward the end of the intervention, we will collect maternal breast milk and infant urine, and assay samples for phthalate metabolite and bisphenol concentrations.
Phase	N/A
Objectives	Aim 1: To assess the feasibility of an intervention designed to reduce infant phthalate and bisphenol exposure Aim 2 (exploratory): To compare urinary phthalate and bisphenol exposure levels in the intervention and non-intervention groups, as well as between mothers and children in the control group.
Methodology	Open-label randomized controlled trial

Endpoint	Participants are enrolled until they have been using the assigned diapers for 3 months, toward the end of which time we will collect maternal breast milk and maternal and infant urine to test for phthalate metabolite and bisphenol concentrations
Study Duration	1 year (allows for 6 months of data collection among 10 participants and 6 months of data analysis).
Participant Duration	3 months
Population	We will recruit 10 participants who are already enrolled in the NYU CHES study at the Brooklyn campus. Eligible participants will be ≥ 37 weeks gestation or < 6 months postpartum, carrying a singleton fetus or with a singleton infant, and intending to breastfeed or breastfeeding.
Study Site	NYULH-Brooklyn
Number of participants	10 participants
Description of Study Intervention/Procedure	Half of the participants will be randomly assigned to the intervention group and will receive a three-month supply of phthalate- and bisphenol-free baby products (e.g., wipes, diaper cream) and a subscription to a cloth diaper service.

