Reference Therapy	Half of the participants will be randomly assigned to the control group and provided with a three-month supply of conventional disposable diapers (e.g., Huggies or Pampers) and baby products (e.g., wipes, diaper cream).
Key Procedures	Three-month adherence to diaper assignment and one-time infant urine collection and maternal breast milk collection.
Statistical Analysis	Our primary aim is to assess the feasibility of the intervention; the project is not adequately powered to detect statistically significant differences between groups. However, we will compare distributions of chemicals between the two infant groups to assess the effectiveness of the intervention and also between mothers and children from the control group to assess the relative prevalence of particular bisphenols or phthalates in diet (reflected in maternal breast milk concentrations) vs. baby products (reflected in infant urinary concentrations).

CONFIDENTIAL

Schematic of Study Design

Key Roles

[name], MPH (Principal Investigator)

Assistant Professor, Department of Pediatrics, NYU Grossman School of Medicine
[name]
[contact]
[contact]

[name] (Sub-Investigator)

Pediatrics, Environmental Medicine & Population Health, NYU Grossman School of Medicine
Director and PI of NYU CHES Study
[name]
[contact]
[contact]

[name], MS (Sub-investigator)

Research Scientist, Lab Manager, Department of Pediatrics, Division of Environmental Pediatrics, NYU Grossman School of Medicine
[name]
[contact]
[contact]
(Analyze phthalate and bisphenol levels in urine and breast milk)

[name] (Sub-Investigator)

Research Data Associate, Department of Pediatrics, Division of Environmental Pediatrics, NYU Grossman School of Medicine
[name]
[contact]
[contact]
(Recruitment, consenting, project management, and data collection)

[name] (Study Team Member)

Assistant Professor, Department of Pediatrics, NYU Grossman School of Medicine
[name]
[contact]
[contact]
(Assist in analysis of urine and breast milk)

CONFIDENTIAL

This material is the property of the NYU Langone Health. Do not disclose or use except as authorized in writing by the study sponsor
Behavioral Intervention Template Version: 18 July 2022

1 Introduction, Background Information and Scientific Rationale

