1.2 Rationale

Infants are highly exposed to phthalates and bisphenols, ubiquitous EDCs that have both estrogenic and anti-androgenic activity. Phthalates and bisphenols have been detected in a range of infant care products, including diapers,^{17,18} wipes, baby lotions, soaps, shampoos,¹⁹ and plastic baby bottles.²⁰ Exposure is magnified by infants' high surface-to-volume ratio and by the increased efficiency of dermal absorption via the thin skin surrounding their enlarged genitalia.²¹ This pilot study will test whether intervening on these sources of exposure during the critical period of minipuberty affects infants' body burden of phthalates and bisphenols. If successful, this protocol may be scaled up and eventually evidence may be used to inform regulation of chemicals contained in infant care products and educational outreach programs to protect children's health.

Aim 1: To assess the feasibility of an intervention designed to reduce infant phthalate and bisphenol exposure.

H1: We will successfully recruit participants from within an existing cohort study and collect biosamples from participants and their children in a single follow-up study visit.

Aim 2 (exploratory): To compare urinary phthalate metabolites and bisphenols between the intervention and non-intervention groups, as well as between mothers and children in the control group.

H2: Chemical levels will be higher among infants in the control group vs. the intervention group. There will be no difference in average chemical concentrations between the two groups of mothers. Among controls, different chemicals will be present in breast milk vs. infant urine.

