4.1 Inclusion Criteria

In order to be eligible to participate in this study, an individual must meet all of the following criteria:

1. Enrolled in NYU CHES study at the NYULH-Brooklyn campus
2. Over 18 years of age
3. At least 37 weeks gestation or <6 months postpartum
4. Carrying singleton fetus or having given birth to a singleton infant
5. Intending to breastfeed or breastfeeding
6. English or Spanish speaking
7. Intending to obtain/obtaining pediatric care for infant at the Sunset Park Family Health Center at NYU Langone

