4.2 Exclusion Criteria

An individual who meets any of the following criteria will be excluded from participation in this study:

1. Not enrolled in NYU CHES study from the NYULH-Brooklyn campus
2. Under 37 weeks gestation or having had a preterm birth
3. Carrying multiples or having given birth to multiples
4. Not intending to breastfeed or not currently breastfeeding
5. Not comfortable communicating in English or Spanish
6. Not intending to obtain/obtaining pediatric care for infant at NYULH Sunset Park Family Health Center
7. Under 18 years of age

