6.1 Study Procedures/Evaluations

6.1.1 Study Specific Procedures

Biospecimen Collection:

- Biospecimens (1.8mL of maternal breast milk, 1.8mL of maternal urine, and 1.8 mL of infant urine) will be collected at one study visit approximately 2-3 months after enrollment. Biospecimen collection will occur either after a routine well-visit or at the participant's home. If a home visit occurs, study staff will go to the participant's home. Refer to Section 6.2 for more details.

Data Collection:

- Participant's electronic medical record will be used to monitor when they have delivered.
- Either the infant's medical record or the NYU CHES study records will be used to obtain birth weight and length for analysis.
- NYC CHES study questionnaire data that participants previously completed under the NYU CHES study will be pulled from the NYU CHES study database.

CONFIDENTIAL

- We will create a new database for the Diaper Study where we will store all Diaper Study-related results along with demographic and NYU CHES study questionnaire data to be pulled from the NYU CHES database.

Questionnaire Administration:

- Participants will be asked to complete a brief adherence questionnaire at three postpartum time points.
 - Questionnaire will be administered over the phone by study personnel 2 weeks and 6 weeks after diaper intervention has begun.
 - Questionnaire will also be administered during the single study visit.
- It will take less than 5 minutes to complete questionnaire.
- Questionnaire responses will be entered into REDCap by study personnel.
- The purpose of the questionnaire is to assess if the diaper delivery service is working smoothly for the mother and to gauge adherence to group assignment.
- Questionnaire data collected from this study will be shared with qualified researchers on the NYU CHES study.

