9.4.2 Analysis of the Secondary Endpoints

Our secondary endpoints are concentrations of bisphenols and phthalate metabolites in breastmilk and infant urine. We will perform t-tests to compare distributions of chemicals between the two infant groups to assess the effectiveness of the intervention. We will also assess correlations of concentrations of individual bisphenols and phthalate metabolites between mothers and children from the control group to assess the relative prevalence of these chemicals in diet (measured in maternal breast milk) vs. baby products (infant urine).

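### Infant urine is read as baby-product exposure, but mixed feeding is allowed and no feeding or bottle-use variable is named for collection or analysis

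*Combined protocol and SAP*

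**What the plan says.** The source attribution appears twice. Section 9.4.2 correlates chemical levels between control mothers and infants to assess "the relative prevalence of these chemicals in diet (measured in maternal breast milk) vs. baby products (infant urine"). The Statistical Analysis row of the Protocol Summary makes the same split, "in diet (reflected in maternal breast milk concentrations) vs. baby products (reflected in infant urinary concentrations").

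On feeding, inclusion criterion 5 (section 4.1) reads "Intending to breastfeed or breastfeeding", and exclusion criterion 4 (section 4.2) removes only women "Not intending to breastfeed or not currently breastfeeding". Nothing requires exclusive breastfeeding. Inclusion criterion 3 admits women at "At least 37 weeks gestation or <6 months postpartum", and section 6.3.5 places the sampling visit 2 to 3 months after product use begins.

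On sources, section 1.2 lists infant care products in which these chemicals were found, ending with "and plastic baby bottles". The Protocol Summary describes what the intervention arm receives as "phthalate- and bisphenol-free baby products (e.g., wipes, diaper cream) and a subscription to a cloth diaper service"; controls receive the conventional equivalents. Neither bottles nor formula are named.

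On data, section 6.1.1 plans the specimens, delivery monitoring, birth weight and length, cohort questionnaires completed earlier, and a short survey given three times. The survey's purpose is "to assess if the diaper delivery service is working smoothly for the mother and to gauge adherence to group assignment". Section 9.3 bases the per-protocol set on self-reported compliance, and section 9.4.5 says the sample does not permit covariate control.

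**The concern.** Urine measures what the infant has taken in by all routes. Reading it as the baby-product measure, set against milk as the diet measure, requires that little else enters the infant's body and that what enters through milk can be set aside. The plan secures neither condition.

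A chemical from formula or solid food would appear in the infant's urine and not in the mother's milk. Under section 9.4.2 it would count as coming from baby products. The error runs in the direction of H2, which expects different chemicals in milk and infant urine among controls, so the observed pattern could not tell the two explanations apart. Section 1.2 says the evidence may eventually inform regulation of chemicals in infant care products, so the attribution matters even in a pilot.

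The comparison of infants between arms is also exposed. With 5 infants per arm, a chance difference in feeding could move it, and no named variable would reveal that.

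**Working it through.** The plan gives no figure to reproduce: the sample size is budget-based (section 9.4.5), and no feeding rate, expected concentration or standard deviation is stated. The check sets the sections side by side and then gives the scale under stated assumptions.

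**Age at sampling.** Entry at under 6 months, plus 2 to 3 months of product use, puts the oldest infants at just under 6 + 3 = 9 months. Solid food is therefore possible for late entrants. Infants enrolled before birth would be sampled at about 2 to 3 months.

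**Could any named variable show feeding mode during product use?**
- Birth weight and length: no.
- Earlier cohort questionnaires: for women enrolled before delivery, no, because the feeding had not yet happened. For postpartum entrants they might cover some earlier feeding; their content is not described.
- Adherence survey: its stated purpose is delivery logistics and group adherence. The form is a separate attachment (section 18) and is not shown.
- Maternal urine: it measures the mother's exposure, not how the infant is fed.
- Section 9: no feeding variable enters any analysis or defines any analysis set.

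**Scale.** Let p be the share of infants who are mixed- or formula-fed. This is an assumption, with infants taken as independent and p equal in both arms.
- At least 1 of 5 control infants affected: 1 - (1 - p)^5. At p = 0.1 this is 1 - 0.9^5 = 1 - 0.590 = 0.410.
- Arms differ by 2 or more affected infants: the sum of P(X = i)P(Y = j) over |i - j| ≥ 2, with X and Y each binomial(5, p). At p = 0.5, X - Y + 5 is binomial(10, 0.5), which gives 1 - (252 + 2 × 210)/1024 = 0.344.

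| p (assumed) | At least 1 of 5 controls affected | Arms differ by 2 or more |
|---|---|---|
| 0.1 | 41% | 10% |
| 0.2 | 67% | 22% |
| 0.3 | 83% | 30% |
| 0.5 | 97% | 34% |

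**What the control correlation can carry.** With 5 pairs the two-sided 5% critical value is |r| = t/√(3 + t²) with t = 3.182, which is 0.88. An observed r of 0.5 has an approximate 95% interval of tanh(0.549 ± 1.96/√2), or -0.68 to 0.96. The correlation cannot separate sources by itself, even if every infant is fed only breast milk.

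**The case against.** The other side has several sound points.

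- **Bottles.** A reader might infer that counting bottle exposure as baby products is an error. Section 1.2 itself lists bottles among infant care products, so it fits the protocol's broad label. What stands is narrower: bottles are not among the named examples of supplied products, and those are an open list. Formula and solids are the clear misattribution.
- **Whole diet.** A reader might infer that the plan equates milk with everything the infant eats. The text does not say so, and diet could mean the mother's diet passing into milk. On either reading infant urine is still labelled as the product measure.
- **Data not collected.** The documents do not support saying that feeding will go unrecorded, because the survey form and cohort questionnaires are not shown. They support only that no such variable is named as data or used in an analysis.
- **A likely imbalance.** If exactly 4 of 10 infants were bottle-fed, the chance of a 3-1 or 4-0 split would be 2 × (50 + 5)/210 = 52%. That is the largest value for any count. For 1, 2, 3, 4 and 5 such infants, the chance that the arms differ by 2 or more is 0%, 44%, 17%, 52% and 21%. Nothing in the documents singles out 4.
- **Lost pairs.** A mixed-fed pair still has valid milk and urine measurements. Only the source attribution fails.

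It is also fair that Aim 2 is exploratory and that section 9.4.5 already disclaims covariate control. That limits the consequence. It does not justify the attribution, and recording and listing feeding needs no model.

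**Conclusion.** The point holds as a problem of interpretation and data collection. Followed as written, section 9.4.2 and the Protocol Summary would credit baby products with chemicals that reached the infant through formula, solid food or milk, and no named variable would show where this had happened. The milk route applies even to infants fed only breast milk, so restricting the comparison to them would not isolate product exposure.

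The size rests on an assumed share of mixed- or formula-fed infants. Over 10-50%, the chance that at least one control infant is affected is 41-97%, and the chance of a between-arm difference of 2 or more is 10-34%. How far concentrations would shift cannot be computed from the documents. The feasibility endpoint is unaffected.

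**What to change.** 1. Add two items to the two telephone surveys and the visit form, unless the unseen survey already has them: feeding since the last contact (breast milk only, mixed, formula, solids), and bottle use, including bottles of expressed milk. At the visit, ask about bottle use in the 24-48 hours before urine collection.
2. List the answers by arm and by control pair beside the infant results.
3. Reword section 9.4.2 and the Protocol Summary, for example: infant urine measures total exposure from all sources; evidence on the supplied products comes from comparing infants between arms; the control milk-urine comparison is descriptive and does not apportion exposure between diet and products.

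Do not restrict the analysis to infants fed only breast milk. Their urine still carries chemicals swallowed with milk or from bottles of expressed milk, and losing pairs raises the critical |r| from 0.88 with 5 pairs to 0.95 with 4 and 0.997 with 3.

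The cost is two questions in a survey of under 5 minutes, a short text change that needs ethics board approval (section 12.2), and a weaker diet-versus-products statement. The items need to be in place before sampling, because recent bottle use cannot be recovered reliably afterwards.

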9.4.3 Safety Analyses

There is no risk associated with the intervention being implemented in this study, so there will be no safety analysis.

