7.2.2 Relationship to Study Intervention

The clinician's assessment of an AE's relationship to study intervention is part of the documentation process, but it is not a factor in determining what is or is not reported in the study. If there is any doubt as to whether a clinical observation is an AE, the event should be reported. All AEs must have their relationship to study intervention assessed. In a clinical trial, the study intervention must always be suspect. To help assess, the following guidelines are used.

- **Related** – *The AE is known to occur with the study intervention, there is a reasonable possibility that the study intervention caused the AE, or there is a temporal relationship between the study intervention and event. Reasonable possibility means that there is evidence to suggest a causal relationship between the study intervention and the AE.*
- **Not Related** – *There is not a reasonable possibility that the administration of the study intervention caused the event, there is no temporal relationship between the study intervention and event onset, or an alternate etiology has been established.*

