7.3 Time Period and Frequency for Event Assessment and Follow-Up

The occurrence of an AE or SAE may come to the attention of study personnel during study visits and interviews of a study participant presenting for medical care, or upon review by a study monitor. All AEs including local and systemic reactions not meeting the criteria for SAEs will be captured on the appropriate RF. Information to be collected includes event description, time of onset, clinician's assessment of severity, relationship to study intervention (assessed only by those with the training and authority to make a diagnosis), and time of resolution/stabilization of the event. All AEs occurring while on study must be documented appropriately regardless of relationship. All AEs will be followed to adequate resolution.

Any medical condition that is present at the time that the participant is screened will be considered as baseline and not reported as an AE. However, if the study participant's condition deteriorates at any time during the study, it will be recorded as an AE. UPs will be recorded in the data collection system throughout the study.

Changes in the severity of an AE will be documented to allow an assessment of the duration of the event at each level of severity to be performed. AEs characterized as intermittent require documentation of onset and duration of each episode.

CONFIDENTIAL

The PI will record all reportable events with start dates occurring any time after informed consent is obtained until 7 (for non-serious AEs) or 30 days (for SAEs) after the last day of study participation. At each study visit, the investigator will inquire about the occurrence of AE/SAEs since the last visit. Events will be followed for outcome information until resolution or stabilization.

All unresolved adverse events should be followed by the investigator until the events are resolved, the subject is lost to follow-up, or the adverse event is otherwise explained. At the last scheduled visit, the investigator should instruct each subject to report any subsequent event(s) that the subject, or the subject's personal physician, believes might reasonably be related to participation in this study. The investigator should notify the study sponsor of any death or adverse event occurring at any time after a subject has discontinued or terminated study participation that may reasonably be related to this study.

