7.4 Reporting Procedures – Notifying the IRB

7.4.1 Adverse Event Reporting

At each contact with the subject, the investigator must seek information on adverse events by specific questioning and, as appropriate, by examination. Information on all adverse events should be recorded immediately in the source document. All clearly related signs, symptoms, and abnormal diagnostic procedures results should be recorded in the source document, though should be grouped under one diagnosis.

All adverse events occurring during the study period must be recorded. The clinical course of each event should be followed until resolution, stabilization, or until it has been determined that the study treatment or participation is not the cause. Serious adverse events that are still ongoing at the end of the study period must be followed up to determine the final outcome. Any serious adverse event that occurs after the study period and is considered to be possibly related to study participation should be recorded and reported immediately.

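### Section 9.4.3 rules out any safety analysis because the intervention is said to carry no risk, so the adverse events that Section 7 requires to be collected have no planned summary by arm

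*Combined protocol and SAP*

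**What the plan says.** Section 9.4.3 consists of one sentence: "There is no risk associated with the intervention being implemented in this study, so there will be no safety analysis".

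Section 7 sets out full AE collection:
- Section 7.4.1: "At each contact with the subject, the investigator must seek information on adverse events by specific questioning and, as appropriate, by examination". It adds: "All adverse events occurring during the study period must be recorded".
- Section 7.3: "All AEs including local and systemic reactions not meeting the criteria for SAEs will be captured on the appropriate RF". Onset, severity, relationship and resolution are to be collected for each event.
- Section 7.2.2: "All AEs must have their relationship to study intervention assessed. In a clinical trial, the study intervention must always be suspect".

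Other sections describe the risk differently. Section 1.3.1 says the intervention adds no excess risk. Section 4.3 expects risk no greater than minimal for mother, fetus and neonate, and gives the common use of both diaper types as the reason. Section 8 calls the risk of participation minimal, uses this to justify having no data and safety monitoring board, and provides for an internal monthly review of safety data with reporting to the IRB.

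On withdrawals, Section 4.7.1 lets the investigator end participation for an AE. Section 4.7.2 replaces a participant who withdraws between consent and specimen collection, and Section 9.4.6 puts the replacement in the same group. Section 6.3.6 provides for no evaluations at withdrawal. Section 9.4.4 plans the percentage completing the study and average self-reported adherence by arm.

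**The concern.** The protocol requires a body of data to be collected and judged, and its analysis section then discards those data on a premise stronger than the protocol's own risk language. That premise is the only reason given for the omission.

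Two things are at stake. First, the arms receive different diapers and baby products (Section 5.1), and Section 1.2 says a successful protocol may be scaled up. Anyone planning the larger study would want to know which events occurred in which arm, and the plan produces no such output. Second, the replacement rule can conceal the information. A participant whose participation ended because of an AE could be replaced in the same arm, and the planned retention and adherence figures carry no reasons.

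**Working it through.** The plan states no safety figure, so there is nothing to reproduce. The check is a comparison of sections, followed by a short calculation of what 5 infants per arm can show.

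**1. Risk wording.** Section 1.3.1 claims no excess risk from the intervention, Sections 4.3 and 8 claim minimal risk, and Section 9.4.3 claims none. The first is relative to usual products and the second is an upper bound. Neither amounts to the third.

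**2. Following one AE through the plan.** It is elicited (7.4.1), recorded with onset, severity and resolution (7.3), judged for relationship (7.2.2) and seen in the monthly review (8). It then reaches Section 9. Sections 9.1 and 9.4.1 to 9.4.5 cover chemical concentrations, completion, adherence and baseline characteristics. None tabulates AEs, and 9.4.3 excludes doing so.

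**3. Following one withdrawal for an AE.** Participation may be ended (4.7.1), no evaluation is done (6.3.6), a replacement may enter (4.7.2) in the same arm (9.4.6), and Section 9.4.4 reports completion and adherence. The reason may be in the AE record, but it is in no planned analysis.

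**4. What 5 per arm can show.** Inputs: 5 per group and 10 in total (Section 9.4.5). With zero events in n infants, the exact two-sided 95% upper limit is 1 − 0.025^(1/n).
- n = 5: 1 − 0.025^(1/5) = 0.522, or 52%.
- n = 10: 1 − 0.025^(1/10) = 0.308, or 31%.

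Even a study with no events could not support a statement of no risk.

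**5. Why a listing and not a test.** The two-sided Fisher p-value for 0 of 5 against k of 5, with k of 3 or more, is 2 × C(5,k)/C(10,k).
- 0 v 3: 2 × 10/120 = 0.167.
- 0 v 4: 2 × 5/210 = 0.048.
- 0 v 5: 2 × 1/252 = 0.008.

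The only other splits reaching 0.05 are 1 v 5 and the mirror images. The documents give no event rates. Under assumed rates, Fisher power at the 5% level is 2% (10% v 30%), 12% (10% v 50%) and 54% (10% v 80%). Events could still plausibly occur and be worth listing: the chance of at least one affected infant in an arm of 5 is 1 − 0.9^5 = 41% at an assumed 10% rate and 1 − 0.7^5 = 83% at an assumed 30%.

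**The case against.** The best defence is that this is an open-label pilot of 10 pairs, in which every event is examined individually under Sections 7.2.2 and 7.3 and reviewed monthly, along with drop-out rates, under Section 8. Section 9.4.3 speaks only of risk from the intervention, which is close to the wording of Section 1.3.1, and Section 7 still contains unedited template text. The conflict may therefore be loose drafting. Feasibility is also defined in H1 and Section 3.2.1 as recruitment, product use and specimen collection, not tolerability, and problems serious enough to cause stopping or switching would affect the figures in Section 9.4.4.

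Much of this stands, and it rules out several stronger readings that a reader might infer:
- *Safety would go unexamined.* It would not. Only the end-of-study summary by arm is missing.
- *Nobody would ask about AEs, because the contacts in 6.3.3 to 6.3.5 list no AE question.* Section 7.4.1 already imposes that duty at each contact. The adherence survey is a separate attachment that is not available here, so its content is unknown.
- *Skin reactions are a likely reason for stopping.* The documents do not say so. They mention local and systemic reactions in general, and Section 4.3 says both diaper types are commonly used in this population.
- *The 52% limit measures the harm of the omission.* It does not. It would be the same with or without a table, and shows only that this sample cannot establish absence of risk.

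The defence does not answer the remaining point. Small numbers argue against testing, not against listing, and Section 9.4.4 would show that someone left or did not adhere, but not why.

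**Conclusion.** The point holds in a narrow form. Section 9.4.3 conflicts with the minimal-risk wording of Sections 4.3 and 8 and leaves the data required by Section 7 without any planned summary by arm. An AE that led to withdrawal and replacement would not be visible as the reason in any planned analysis.

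The severity is minor. No endpoint, sample size or stated figure changes, and individual events are still assessed and reviewed. The conclusion rests on the text alone. The upper limits need only the 5-per-arm design, while the power and event-probability figures depend on assumed rates and serve only to show that a formal test would add little.

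**What to change.** Replace Section 9.4.3 with a statement such as: all AEs will be listed and counted by assigned group, giving the number of infants affected, severity and relationship to the intervention, and including participants who withdrew or were replaced; no hypothesis tests will be done. Maternal events can be listed in the same way.

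Reconcile the risk statements in Sections 1.3.1, 4.3, 8 and 9.4.3 so that they say the same thing.

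Optionally, add a cross-reference to the AE inquiry of Section 7.4.1 in the schedule entries 6.3.3 to 6.3.5.

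The cost is one sentence and one small table. No data are needed beyond those Section 7 already requires.
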